### **b. Quality Control Method Monitoring Plan:**

The investigator must maintain source documents for each patient in the study, consisting of case and visit notes containing demographic and medical information, and the results of any other tests or assessments. All information on the eCRFs must be traceable to these source documents in the patients file. The investigator must also keep the original informed consent form signed by the parent/legal guardian.

The investigator must give the monitor access to all relevant source documents to confirm their consistency with the eCRF entries.

Routine independent monitoring visits shall occur one or more times during the period after study initiation but before study closeout. Guidelines for scheduling monitoring visits shall be determined according to the stage of development, complexity of the study, the rate of subject accrual and other factors. Monitoring visits are conducted for routine monitoring only and are intended to ensure that the

protocol and applicable regulatory requirements are being followed, that subjects' rights and safety are protected, and to confirm data integrity and quality.

The CRC representative will perform reviews as follows:

100% source and data verification of 1st patient Visit 1 at all sites. Subsequently, 10% of the records will be reviewed quarterly at all sites. If significant discrepancies exist (more than 5% of responses), retraining and comprehensive crosschecking will be performed.

**c. Data Analysis Plan**

We employed a block randomization design for each site to ensure balanced distribution of treatment groups. Baseline characteristics and the duration of the O2 management in RHO and control groups will be compared using the independent sample test for continuous measures and the  $\chi^2$  test for categorical measures. To compare the oximetry in the sleep study and the home recording studies, we will use generalized estimating equation (GEE) gamma regression models for longitudinal count data. Gamma regression models are appropriate for highly skewed measurement or count outcome data, and exponentiating the regression parameters from these models gives estimates of the percent change in the mean outcome corresponding to a change in the independent variable.

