## **1. Abstract**

This research protocol describes a randomized control trial to compare two different methods of managing home oxygen therapy in premature infants. This is a multicenter study involving 9 centers. We plan to enroll a total of 196 infants, of which 68 will be from Boston Children's Hospital (BCH). The current standard for oxygen management includes brief assessments of a patient's oxygen saturation status during monthly clinic visits. The patient's oxygen status between visits is assumed to be acceptable; although it is possible for significant hyperoxia or hypoxia to occur, providers have no data to help with decision-making. In many centers, final steps before discontinuing home oxygen therapy (HOT) often include polysomnography (PSG), which can be costly and requires the inconvenience of rehospitalization. Advances in data storage and pulse oximetry technology have expanded potential uses for recorded home oximetry (RHO) in the accurate assessment of hypoxemia. At Boston Children's Hospital, we have pioneered the use of recorded home oximetry (RHO) in other research protocols, and shown that it can be a simple and convenient method for parents to transmit oximetry data to providers.

In this trial, we will randomize premature infants who require HOT at time of discharge from the NICU, who are referred for follow-up at the Center for Healthy Infant Lung Development. At the time of their first outpatient appointment, infants will be randomized to one of two treatment arms:

**Arm A (“Standard therapy”):** Infants' oxygen will be increased, decreased, or maintained based on brief structured assessments during monthly clinic visits. Polysomnograms will be utilized prior to final discontinuation of oxygen. RHO will only be utilized on the night prior to and during the polysomnogram to compare these two modalities.

**Arm B (RHO):** Infants will have the same monthly clinic assessments as in Arm A, but also will utilize RHO to potentially increase, decrease or maintain oxygen between monthly visits. Parents will transmit a minimum of 25 hours (1500 minutes) of stored RHO data (approximately 4 days, 8 hours per day) every 4-7 days. Changes in oxygen needs will be made based on standardized objective criteria. To determine discontinuation of oxygen, RHO will be utilized instead of polysomnography.

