**- Baseline Visit ( First Initial Visit): V0**  
**(For all patients in ARM A and ARM B )**

After confirming eligibility and obtaining the consent form, growth parameters, nutrition notes, NICU discharge summary, demographics and PedsQL survey will be obtained at this visit.

Medical records will be transferred to UMass using methods to ensure data safety, for abstraction by study staff. [name] will train study staff in abstraction of medical records.

Each site PIs will perform the baseline growth assessment and perform randomization at time of enrollment. We will perform block randomization to ensure equal distribution within each site.

Study staff at BCH will ask parents to complete a PedsQL at the initial (baseline) clinic visit. Research staff at BCH will hand the questionnaire to the parent for self-report in order to minimize response bias and standardize methods. If for some reason the PedsQL is not completed in clinic, staff at BCH or UMass will contact the family to complete the survey over the phone shortly after the visit. Growth and nutrition information from this visit will also be recorded.

At the end of the visit, contact information will be confirmed, and the parent will be reminded about the next planned phone/clinic visit and interview.

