**d. Statistical Power and Sample Considerations**

*Analyses for Aim 1:*

Aim 1: To evaluate the effects of a data-driven HOT management protocol on parent(s) quality of life.	Hypothesis 1.1: Parents of patients weaned from HOT using a data-driven management protocol will have improved quality of life compared to their status at time of NICU discharge compared to patients weaned using the current standard HOT management protocol.
--	--

For the impact of oxygen management protocol on the family's emotional health, we will use the PedsQL. We are performing these scales at the beginning of the outpatient HOT management process, to establish a baseline, and then will repeat these measures at the end of the HOT weaning process (6 months after discontinuation of HOT). We will test the association of oxygen management protocol with change in each measure using the Student's *t*-test to analyze the difference between intervention groups. Multivariate linear regression models will adjust for potential confounding variables, including parent and medical attributes.

Power calculation for hypothesis 1.1:

Power calculations are based on the primary analyses (t-test). A sample size of 130 will give 80% power, with 0.05 two-sided type I error rate, to detect a 20% absolute difference in emotional role limitation on the PedsQL, which we consider to be clinically significant.

*Analyses for Aim 2:*

Aim 2: To evaluate the impact of a data-driven HOT management protocol on duration of HOT.	Hypothesis 2.1: A data-driven HOT protocol will shorten duration of HOT therapy compared to the current standard HOT management protocol.
---	--

For the primary outcome, duration of HOT, the interval from date of first outpatient clinic visit/enrollment to discontinuation of HOT will be determined. Mean duration of HOT between the two groups will be compared.

Based on our experience weaning over 130 premature infants from O2, we expect the mean duration of HOT in our standard treatment group (clinic-based weaning) to be 144+/-66 days, and we anticipate that RHO weaning strategies will decrease the median duration by 25% (36 days) to 108 days. A total sample of 98 infants per group provides 97% power to detect this effect of the RHO strategy (two-tailed, alpha=0.05, see Table 2).

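### Randomisation is blocked by site, but neither primary test includes site; duration has no baseline covariate and PedsQL uses a change score instead of ANCOVA, at a small cost in precision

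*Combined protocol and SAP*

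**What the plan says.** **Design.** The Abstract says "This is a multicenter study involving 9 centers" and "We plan to enroll a total of 196 infants, of which 68 will be from Boston" Children's Hospital. The baseline-visit text in section 4f says "We will perform block randomization to ensure equal distribution within each site", and section 5c repeats this: "We employed a block randomization design for each site to ensure balanced distribution of treatment groups". Block size is not given.

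**Duration of HOT.** Section 5c says "the duration of the O2 management in RHO and control groups will be compared using the independent sample test for continuous measures". Section 5d adds "Mean duration of HOT between the two groups will be compared". No site term, covariate or adjusted model is named for this outcome.

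**PedsQL.** Section 5d says "We will test the association of oxygen management protocol with change in each measure using the" Student's t-test, and the power paragraph confirms that this test is primary: "Power calculations are based on the primary analyses (t-test"). Section 5d also plans linear regression adjusting for parental and medical characteristics. Site and baseline PedsQL are not named among them.

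**Data in hand.** The visit schedules in section 4f collect the oxygen setting and PedsQL at V0 in both arms. The paragraph on confounding variables in 4f lists further demographic and severity data, but ties none of them to a primary model.

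**The concern.** Blocking within site makes the arms nearly equal in size at each site, so differences between sites largely cancel out of the treatment comparison. A two-sample test does not know this. It leaves the between-site variation in its error term and so reports a standard error larger than the true sampling variability of the estimate. The nominal 5% test then runs below 5%, and intervals are wider than they need be.

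Two related efficiencies are also left unused. Starting oxygen flow should predict duration, because the weaning scheme under Table 1 sets the number of steps an infant must pass through, yet it does not enter the duration comparison. For PedsQL, a change score subtracts the whole baseline, whereas ANCOVA lets the data set the weight.

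What is at stake is precision on both primary outcomes, and the usual principle that the analysis should reflect the randomisation. The validity of the trial is not at stake.

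**Working it through.** **1. The plan's own figure.** Inputs from section 5d and Table 2: 98 per group, difference 36 days, SD 66 days, two-sided 0.05.

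- SE = 66 × √(2/98) = 9.43 days. Power = Φ(36/9.43 − 1.96) = 96.8%, which reproduces the stated 97%.
- With the 85% completion named in the Table 2 caption (83.3 per group): SE = 10.23 days, power 94.1%. The stated 97% therefore holds only with no loss. That is a separate matter, but 94.1% is the fairer base for what follows.

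**2. Site: the limiting formula.** The documents give no site ICC, so 0.05, 0.10 and 0.15 are assumed. With exact balance in every site and all ICC variance removed:

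- True type I error = 2 × [1 − Φ(1.96/√(1 − ICC))] = 4.4%, 3.9%, 3.4%.
- Excess interval width = 1/√(1 − ICC) − 1 = 2.6%, 5.4%, 8.5%.

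These overstate the effect here, for two reasons. One site holds 68 of 196 infants. If the other 128 are spread evenly (16 each, assumed), the between-site variance expected in the pooled sample is only 1 − [(68/196)² + 8 × (16/196)²] = 1 − (0.120 + 0.053) = 0.83 of its nominal value. Loss to follow-up also disturbs the within-site balance.

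**3. Site: simulation.** Assumed: 68 + 8 × 16 infants, blocks of 4, normal outcomes, total SD 66, losses at random. Completion of 85% is from Table 2. The unadjusted t-test is compared with a linear model containing site. Ranges span repeated runs of at least 6,000 trials; with 6,000, the Monte Carlo error on a 5% rate is √(0.05 × 0.95/6000) = 0.3 points.

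| Assumed ICC | Type I error, unadjusted | Intervals too wide by | Power, unadjusted v with site |
|---|---|---|---|
| 0 | nominal | none | 93.7% v 93.6% |
| 0.05 | about 4.9% | 0.5-3% | 94.1% v 94.4% (about 0.4 points) |
| 0.10 | 3.9-4.2% | about 4% | 94.7% v 95.5% |
| 0.15 | 3.7-3.8% | 5-6% | 95.1% v 96.5% (1.4-1.5 points) |

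At ICC 0.10 the true SD of the estimate is 9.74 days unadjusted and 9.72 with site, while the mean reported SE is 10.13 and 9.73. For site, then, the estimate itself is hardly less precise. The loss lies in the reported standard error.

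**4. Starting flow and duration.** If covariates explain a share f of the variance, the SD becomes 66 × √(1 − f). At 83.3 per group, power is 94.1% (f = 0), 95.1% (0.05), 96.0% (0.10) and 97.6% (0.20).

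An illustration of f for flow: eligible flows run up to 1 L/min, and weaning halves the flow to 125 cc/min, then goes to night only, then off. Starting flows of 125, 250, 500 and 1000 cc/min therefore need 2, 3, 4 and 5 steps. Assume equal numbers at each flow (variance of steps 1.25), 30 days per step in Arm A and 7 in Arm B (mean 18.5). A common flow term then explains 18.5² × 1.25 = 428 of 66² = 4356, or about 10%.

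**5. PedsQL.** With equal variances σ² at both times and baseline correlation r, the change score has variance 2(1 − r)σ² and ANCOVA (1 − r²)σ². The ratio is (1 + r)/2.

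| Assumed r | 0.4 | 0.5 | 0.6 | 0.7 | 0.9 |
|---|---|---|---|---|---|
| ANCOVA variance lower by | 30% | 25% | 20% | 15% | 5% |

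Section 5d gives no SD for PedsQL, so this cannot be turned into points of power.

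**The case against.** The other side has a good deal in its favour.

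- A reader might infer that the PedsQL test ignores baseline. It does not: it analyses change, so baseline enters by subtraction. Change score and ANCOVA are both unbiased in a randomised trial, and the choice between them is one of efficiency. If r is 0.9, the gain is only 5%.
- A reader might infer that no adjustment is planned. A PedsQL regression is planned and covariates are collected for it. What stands is narrower: the regression is not primary, names neither site nor baseline score, and has no counterpart for duration.
- A reader might take the wide practice variation reported in section 3 as evidence of a large site effect. It comes from a national survey of usual practice, not from these nine sites. The trial also imposes common weaning criteria and steps, and Arm B recordings are analysed centrally. Case mix and access to polysomnography may still differ, but the documents support no particular ICC. If sites do not differ, nothing is lost by omitting site.
- The power cost for duration is small in a trial with about 94% power after losses.

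All of this limits the size of the point. None of it gives a reason to leave the randomisation stratum and the V0 values out of the primary models.

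**Conclusion.** The point holds as a conditional matter of efficiency. Neither primary test includes the blocking factor, duration is compared without any baseline covariate, and PedsQL uses a valid but less efficient form of baseline adjustment.

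If sites differ, the duration test is conservative by the modest amounts in the simulation table, and at an ICC near zero there is no material difference. The larger possible gains are from starting flow (about 2 points of power if f is 0.10) and from ANCOVA for PedsQL. The ICC, f, r, block size and spread of infants over the smaller sites are all assumed, because the documents give none of them.

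A reader might go further and conclude that the planned tests are invalid or inflate false positives. The documents do not support that: the error runs in the conservative direction and introduces no bias. This is an improvement worth making because it is free, not a defect that threatens the conclusions.

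**What to change.** Amend sections 5c and 5d as follows.

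- **Duration, primary:** a linear model of duration on arm, site and V0 oxygen flow, reporting the adjusted difference in means with its 95% interval. Entering flow on a log2 scale would match the halving steps.
- **PedsQL, primary:** an ANCOVA of the post-wean score on arm, baseline PedsQL and site. The amendment should name one post-wean time point, since section 4f gives 3 months and section 5d gives 6.
- **Small sites:** pool them by a rule fixed before outcome data by arm are seen.
- **Sensitivity:** keep the unadjusted two-sample test for duration and the t-test on PedsQL change.
- **Additional PedsQL regression:** list its covariates in advance, including site and baseline score.

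The cost is analysis-plan wording. The visit schedule already collects the V0 flow and PedsQL, site is known for every infant, and the sample size does not change.

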#### **4.e. Definition of Primary and Secondary Outcomes/Endpoints**

Primary measures: (a) Total duration of home oxygen therapy (HOT) from the first outpatient pulmonary appointment to discontinuation of supplemental O2; and (b) Parent quality of life, assessed by differences in the post-weaning PedsQL baseline.

Secondary measures: (a) Number of rehospitalizations and emergency department visits from 1st clinic visit through 6 months after discontinuation of HOT; (b) Change in weight and weight-for-length z-score from 1st clinic visit to 6 months after discontinuation of HOT; and (c) For patients who will receive a sleep study, percent time below designated O2 saturation thresholds (<96%, <93%, and < 90%) will be calculated from both RHO and from the polysomnogram data. The number of desaturation events (defined as saturation drops below 90% for >10 seconds and > 20 seconds) will also be analyzed.

Duration of HOT was chosen as a primary outcome since it is the primary driver of caregiver emotional and financial health for families of infants on HOT. This outcome was driven by input from families themselves, through a process of including important stakeholders in the protocol development process. The PedsQL was chosen as an additional primary outcome because it is validated, accurate scale in which scores correlate with maternal psychiatric symptoms, poor child health, poor child adjustment, and increased child hospitalizations.

This protocol focuses on patient-centered outcomes that may demonstrate non-inferiority from a medical safety perspective, but may improve quality of life. While families place a priority on treatment strategies that optimize health, when there are multiple choices without a clear medically superior choice, then the impact of specific treatment choices on quality of life will help drive decision-making.

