**For patients randomized to HRO-based weaning:**

We will determine the number of seconds/hour with saturation >96, < 93, and < 90%, and the percentage of time below these thresholds for each recording interval (minimum 4-day epochs during weaning for

randomized infants, and 12 hour epochs for all infants both on the night before and during PSG) using target saturation limits defined in Table 1 to determine whether weaning can proceed.

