**For PSG evaluations:**

Infants will “pass” the PSG when they can maintain O2 saturation >93% for >95% of the time, with a minimum of 8 hours of nocturnal recording.

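### The gamma GEE planned for the RHO–PSG comparison has no zero rule and no recording-time offset, so desaturation-event ratios can be wrong if zero records are dropped or recording hours differ

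*Combined protocol and SAP*

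**What the plan says.** Section 5c (Data Analysis Plan) covers the comparison of the sleep-study and home recordings: "we will use generalized estimating equation (GEE) gamma regression models for longitudinal count data". It justifies the choice by stating that "Gamma regression models are appropriate for highly skewed measurement or count outcome data", and adds that "exponentiating the regression parameters from these models gives estimates of the percent change in the mean outcome", which implies a log link. It does not state a working correlation, an offset or the treatment of zero values.

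Section 4.e, secondary measure (c), defines what is compared. Percent time below 96%, 93% and 90% "will be calculated from both RHO and from the polysomnogram data". For events it says: "The number of desaturation events (defined as saturation drops below 90% for >10 seconds and > 20 seconds) will also be analyzed". That is a number of events with no time denominator.

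Two places in section 4f bear on recording length. Under HRO-based weaning the plan says "We will determine the number of seconds/hour with saturation >96, < 93, and < 90" percent, and sets "12 hour epochs for all infants both on the night before and during PSG". Under PSG evaluations an infant can pass "with a minimum of 8 hours of nocturnal recording".

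**The concern.** A gamma distribution is continuous and strictly positive, whereas an event count is discrete and can be zero. Zero nights are plausible here. Arm A infants reach PSG only at the last stage before oxygen is stopped, and a pass requires saturation above 93% for more than 95% of the time. The documents give no event rate, so the share of zeros is unknown. Percent time and seconds per hour below 90% can also be zero.

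Two things could then go wrong.

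- **Zeros.** An analyst whose gamma routine refuses zeros may drop those records. That removes the nights with the best oxygenation from both methods, and more of them from the method with the lower mean.
- **Exposure.** Raw counts from recordings of different length are not comparable without a time denominator.

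The stated overall objective includes removing the need for PSG, and this is the only head-to-head analysis of the two methods that the plan specifies. At equal hours, dropping zeros moves a real difference toward apparent agreement. Unequal hours can create a difference that does not exist.

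**Working it through.** The plan states no ratio, power or sample size for this comparison, so there is no figure of its own to reproduce.

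**Inputs from the documents:** nominal 12 h epochs on both nights and an 8 h minimum for a PSG pass (section 4f); 98 infants per arm with 85% completing (section 5d), so 98 × 0.85 ≈ 83 paired infants.

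**Assumed, because the documents are silent:** 0.1, 0.3, 1 and 3 events per hour, and Poisson counts with a gamma-distributed infant effect of variance 1.5 shared by both methods.

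**1. Zeros kept, equal hours.** With a log link, variance proportional to μ² and independence working correlation, the GEE solves Σ x(y − μ)/μ = 0. A record with y = 0 enters like any other. For a two-method comparison the solution is the ratio of the two sample means, which is also what a Poisson GEE returns. In simulation (120 replicates per setting, gamma GEE, zeros kept, log-hours offset) the median ratio was 0.995 to 1.02 for a true 1.0 and 1.49 to 1.51 for a true 1.5. No fit failed. There is no material bias.

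**2. Zeros dropped, equal 12 h.** The mean of the remaining records is m/(1 − P0(m)), where m = 12 × rate and P0(m) = (1 + 1.5m)^(−1/1.5). For a true ratio t, the ratio obtained is t × (1 − P0(m))/(1 − P0(tm)). With t = 1.5:

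| Events/h | m | P0(m) | P0(1.5m) | Ratio obtained | Simulated median |
|---|---|---|---|---|---|
| 0.1 | 1.2 | 0.503 | 0.418 | 1.5 × 0.497/0.582 = 1.28 | 1.26 |
| 0.3 | 3.6 | 0.290 | 0.229 | 1.5 × 0.710/0.771 = 1.38 | 1.37 |
| 1 | 12 | 0.140 | 0.108 | 1.5 × 0.860/0.892 = 1.45 | 1.46 |
| 3 | 36 | 0.069 | 0.053 | 1.5 × 0.931/0.947 = 1.47 | 1.48 |

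A separate simulation over 0.1 to 1 event per hour gave 1.29 to 1.45. For t = 1.0 the two P0 terms are equal and the ratio stays at 1.0 (simulated 1.00 to 1.04).

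**3. No offset, zeros kept.** The expected count is rate × hours, so the exponentiated coefficient is (true rate ratio) × (RHO hours/PSG hours). For a true ratio of 1.0:

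- 12 h against 12 h: 12/12 = 1.0
- 12 h against 10 h: 12/10 = 1.2
- 12 h against 8 h: 12/8 = 1.5 (simulated 1.50 to 1.54)
- mixed lengths, RHO 8–12 h against PSG 8–10 h: simulated 1.07 to 1.11, with coverage of the 95% interval as low as 58%. If lengths are spread evenly the means are 10 h and 9 h, and 10/9 = 1.11.

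**4. Both problems together.** With 12 h against 8 h, an offset included and zeros dropped, a true 1.0 became 0.85 to 0.97. The pull toward 1 in step 2 is therefore a statement about equal hours only.

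**The case against.** The strongest reply is that GEE uses no likelihood. It needs only a mean model and a variance function, and it accepts zeros. Step 1 bears this out. A separate check with a true ratio of 0.50 and negative binomial means of 2, 3 and 5 gave medians of 0.497, 0.502 and 0.499, with coverage of 93.5% to 94.5%; a negative binomial GEE gave the same. A reader might infer that gamma regression fails at zero and must give wrong ratios. The documents do not support that: they do not say zeros will be dropped, and if zeros are kept and hours are equal the estimate is sound.

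A reader might also take 1.5 as the expected distortion. The plan sets the same 12 h epoch for the night before and for the PSG night, and RHO also runs during the PSG itself. The 8 h figure is a condition for passing, not an analysis window. A ratio of 1.5 needs every home recording at 12 h and every PSG at its 8 h floor.

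Third, percent time and seconds per hour already carry a time denominator, so the offset point concerns event counts only. Fourth, this is the third secondary measure, with no hypothesis, power calculation or decision rule attached. The Background section also expects the two methods to give comparable data, and near a ratio of 1 with equal hours dropping zeros does little.

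All of this limits the point but does not remove it. The plan asserts that gamma suits counts, states no zero rule, and leaves event counts without a time denominator although actual recordings may differ in length. Software differs on zeros: R's gamma family rejects zero values, while the GEE routine used for the simulations here accepts them. As written, the result can depend on the package and on an analyst's unrecorded choice.

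**Conclusion.** The point holds in a limited form. The specified method does not handle desaturation-event counts reliably, because it leaves zeros and recording time undefined.

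- **If zeros are dropped at equal hours,** a true RHO–PSG ratio of 1.5 falls to about 1.28 to 1.45 at 0.1 to 1 event per hour. A true ratio of 1.0 is essentially unchanged.
- **If actual hours differ and no offset is used,** the ratio is multiplied by the ratio of hours: about 1.07 to 1.11 for moderately mixed lengths, 1.2 for 12 h against 10 h, and 1.5 at the extreme.
- **If zeros are kept and hours are equal,** there is no bias.

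The sizes in the first item rest on assumed event rates, dispersion and true ratio; the multiplication by hours does not. The zero-handling gap also touches percent time and seconds per hour, but the offset gap does not. Neither primary outcome is affected, nor are the emergency-visit, rehospitalization or growth comparisons. The point is worth correcting because this is the plan's only specified comparison of the two methods and the correction is nearly free.

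**What to change.** In section 5c:

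- **Desaturation-event counts (>10 s and >20 s):** replace gamma with a negative binomial or Poisson log-link GEE, with robust standard errors, log recorded hours as offset and infant as cluster.
- **Percent time and seconds per hour:** add no offset, since that would divide by time twice. Use a model that accepts zeros, for example a fractional logit GEE for percent time or a quasi-Poisson log-link GEE.
- **All measures:** state that every zero record is kept.
- **Recordings compared:** state which RHO night is set against the PSG, and whether nights are pooled. The Abstract speaks of one night before the PSG, while the text after Table 1 speaks of nights.
- **Justification:** delete the statement that gamma suits count data.

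The cost is a few sentences in the analysis plan. No new data are needed, because recorded hours are already required to compute percent time.
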